Protocol date: October 2018

SYNERGISTIC EFFECT OF EXCLUSIVE ENTERAL NUTRITION FORMULA IN ADDITION TO CORTICOSTEROIDS THERAPY TO INDUCE CLINICAL REMISSION IN PATIENTS WITH CROHN'S DISEASE: A PILOT STUDY INVOLVING A MULTIDIMENSIONAL ASSESSMENT OF POTENTIAL MECHANISMS

Principal Investigator: [name]

Co-PI: [name] MD;

Co-investigators: [name]; [name]; [name]; [name] MD; [name]; [name], NP; [name]; [name]; [name]; [name]; [name]; [name]; [name].

Student: [name]

Farncombe Family Digestive Health Research Institute- McMaster University

Lay Abstract

Crohn's disease (CD) is an inflammatory bowel disease (IBD) characterized by diarrhea, abdominal pain and bleeding. There are several treatment options but the most-widely used for acute therapy are corticosteroids (CS); unfortunately, CS are often associated with severe side effects. The administration of a formula for exclusive feeding (EEN) is well-established as an alternative to CS in children with Crohn's disease (CD). However, this intervention is not routinely used in adults, in part because of uncertainty regarding the magnitude of the benefit of EEN reported in previous studies. In fact, few studies have examined the effects of EEN in adult patients with active CD. We propose that a polymeric formula, provided orally, may help decrease gut inflammation and improve nutritional status through modulation of gut bacteria. We will therefore investigate the effect of exclusive formula feeding therapy in addition to different regimes of CS therapy compared to CS alone in adult patients with active CD, on symptoms and inflammation after 6 weeks of treatment. We will collect information through questionnaires that assess gut symptoms, quality of life, mood changes and dietary patterns. To investigate potential mechanisms, we will collect stool samples to characterize gut bacterial profiles, blood to determine inflammatory markers and evaluate gut movements (motility) before, and after the treatment. We hope that our results will lead to better understanding of the beneficial effect of exclusive formula feeding in addition to CS as a more efficacious alternative than CS alone, and to understand the mechanisms of this therapy.

BACKGROUND

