Crohn's disease (CD) is characterized by inflammation of the gastrointestinal (GI) tract, diarrhea, pain and rectal bleeding¹. Canada has one of the highest prevalences of CD in the world with an estimated incidence rate of 16.3 per 100,000². The pathophysiology of CD is not well understood, but a dysregulated immune response to altered microbiota may play a key role³. Treatment of CD requires a multi-disciplinary approach involving medical therapy, surgery and dietary changes. Corticosteroids (CS) are the first line therapy to induce remission; however, they have adverse effects and 30% of patients can prove to be steroid resistant or dependent⁴. Therefore, alternative therapies that can effectively induce and maintain disease remission without short and long-term side effects are needed⁵.

Exclusive enteral therapy (EEN) involves a liquid diet of elemental or polymeric formula (PF), given exclusively over a prolonged period⁶. Elemental formula contains individual amino acids, while PF is providing intact proteins⁷. Although exclusive enteral nutrition (EEN) is used in children as an alternative to CS to induce remission due to its excellent safety profile⁷, it is not routinely used in adults.

The beneficial effects of EEN in CD were first demonstrated over two decades ago, when O'Morain et al⁸ demonstrated in a controlled study that an elemental diet was as effective as CS in achieving remission in adults with active CD. In particular, EEN was shown to induce the expression of growth factors, promote changes in intestinal permeability and stimulate mucosal healing^{8, 9}. Since then, several studies aimed to investigate this area. Meta-analyses of EEN versus CS have found that, although CS are superior to EEN in

inducing remission, EEN is also efficacious with expected remission rates of up to 60% and provides additional nutritional benefit^{5,10,20}. Although several studies have demonstrated effectiveness of elemental EEN in children, the effect of EEN in adult CD remain controversial^{5,7,20}.

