Potential mechanisms by which EEN might act include relative bowel rest, reduced antigenic load, provision of trophic amino acids, local anti-inflammatory effects, and modification of gut microbiota^{11,20}. However, there is no strong evidence to fully support any one of these mechanisms. A recent meta-analysis²⁰ showed that the effects of the therapeutic formula on specific bacterial strains were variable and inconsistent among studies, possibly due to small sample sizes and methodological limitations. Our preliminary data showed that short term dietary changes improve motility in patients with low-grade gut inflammation²¹. However, the effects of EEN on gastrointestinal transit in adults has not been yet investigated.

Evidence for the effect of EEN on quality of life, an essential patient reported outcome, is particularly scarce. Guo *et al*³⁰ found an improvement of quality of life in 13 patients with CD receiving EEN for 6 weeks. However, it is currently unknown whether EEN is more effective than CS in improving quality of life in adults with CD.

The potentially synergistic effects of adding EEN to CS therapy have not been explored before. Therefore, we designed a randomized controlled trial with the objective to investigate the effect of EEN in addition to different regimes of CS therapy (ECS) compared to CS alone (CS), for decreasing disease activity and improving quality of life in adult patients with CD. We also propose to investigate potential mechanisms underlying any beneficial effect of EEN in CD in the context of concomitant CS therapy.

Hypotheses:

- 1- Six weeks of ECS will be more effective than CS in inducing clinical remission in patients with active CD
- 2- Six weeks of EEN in addition to a short course of CS (ECSC) will have similar efficacy than ECS and reduced number of adverse events
- 3- Six weeks of ECS will lead to beneficial changes in the composition and/or metabolic activity of the intestinal microbiota, gastrointestinal transit and inflammatory burden.

Because the effect size of ECS has not been investigated before, we will perform a pilot study to assess feasibility and calculate estimates of effect size in order to plan a larger trial. Based on the significant number of patients, if the study is feasible, we will consider the sample size estimated through this pilot study for the full trial to minimize the possibility of recruiting additional patients.

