General aim and endpoint: To assess study feasibility and provide estimated effect sizes (point estimates with confidence intervals) for all measures of interest in order to plan an adequately powered study. We will assess recruitment rates and acceptability of treatment in arms involving exclusive enteral nutrition.

Primary outcome and endpoint: To assess the efficacy of 6 weeks of ECS in inducing remission (CDAI <150) compared to treatment with CS in adult patients with active CD (CDAI >220 and either CRP >5 or fecal calprotectin >250 mg/l).

Secondary outcomes and endpoints: To determine the beneficial effect of 6 weeks of ECS as compared to CS in inducing:

1. Clinical disease improvement (drop in CDAI >70 or 100)
2. Improvement in quality of life (using the Inflammatory Bowel Disease Questionnaire (increase IBDQ scores))
3. Biochemical remission (normalization of either serum CRP and/or fecal calprotectin)
4. Changes in microbiota composition (16S sequencing Illumina)
5. Normalization of colonic transit (SHAPE 0-5 markers at day 5)³⁴ among those with altered transit at baseline
6. Decrease in anxiety and/or depression scores (decrease >2 points HAD-A and/or HAD-D scores)
7. Increase in body weight and improvement in nutritional status (increased levels of micronutrients)
8. Decrease of indirect markers of mucosal integrity (IFABP2)
9. Changes in bacterial fermentation profile (SCFAs: acetate (acetic acid), propionate (propionic acid), and butyrate (butyric acid))^{26,27}.
10. Decreased number of adverse events

METHODS

Study design

Protocol date: October 2018

Randomized control trial; 3 arms of treatment: EEN plus standard or short course of CS (ECS, ECSC) vs CS alone (CS) conducted at McMaster University Medical Centre (Figure 1). The study will last 10 weeks and will involve 4 visits. At the screening visit, we will assess clinical history and symptoms, perform a physical exam and complete bloodwork after the informed consent is signed. Randomization will occur at the second visit (pre-treatment), when the inclusion and exclusion criteria and symptoms will be re-assessed, and baseline stool and urine samples will be collected. In addition, we will perform a SHAPE study and patients will be assessed by a dietitian or clinical nutrition support specialist to assess dietary factors and estimate energy needs using the Harris Benedict equation as detailed below.

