Appendix 2-Steroids adverse events assessment (visit 2)

	Yes/no	Comments
1. Moon face		
2. Bloating		
3. Swelling		
4. Weight gain		
5. Increase appetite		
6. Hair loss		
7. Acne		
8. Stretch marks		
9. Insomnia, restlessness and or trouble sleeping		
10. Anxiety or nervousness		
11. Depression		
12. Anger/irritability		
13. Generalized weakness or fatigue		
14. Joint pain		
15. Hot flushes		
16. Visual problems (light sensitivity, decreased visual acuity)		
17. Nausea, vomiting		
18. Diarrhea		
19. Dizziness		
20. Headaches		
21. Hypertension		
22. High glucose levels		

Nestlé Nutrition Flavour Mix

Description

Nestlé Nutrition Flavour Mix is a flavouring powder formulated for use with Peptamen® Vanilla Cup and Modulen® IBD.

Presentation

60g tub (with a 0.6g scoop). Available in 5 flavours: Banana, Lemon & Lime, Chocolate, Strawberry and Coffee.

Indications

ACBS approved, prescribable on FP10 (GP10 in Scotland). For use with Vanilla flavoured Peptamen® and Modulen® IBD.

Ingredients

Banana Flavour

Dextrose, Flavouring (contains Maltodextrin), Maltodextrin, Anti-caking agent (Silicon dioxide), Colour (Curcumin), Sweetener (Sucralose).

Coffee Flavour

Dextrose, Soluble Coffee solids, Anti-caking agent (Silicon dioxide), Colour (Caramel E150c), Sweetener (Sucralose).

Strawberry Flavour

Dextrose, Flavouring (contains Maltodextrin), Acidity regulators (Lactic acid, Acetic acid), Stabiliser (Gum arabic), Preservative (Sulphur dioxide), Anti-caking agent (Silicon dioxide), Colour (Beetroot red), Sweetener (Sucralose).

Lemon & Lime Flavour

Dextrose, Flavouring (contains Maltodextrin), Modified starch, Antioxidant (E320), Citric acid, Anti-caking agent (Silicon dioxide), Colour (Curcumin), Sweetener (Sucralose).

Chocolate Flavour

Dextrose, Flavouring (contains Maltodextrin), Stabilisers (Glycerine, Gum arabic), Molasses, Anti-caking agent (Silicon dioxide), Colour (Caramel E150c), Sweetener (Sucralose).

All Flavours: Milk, Egg, Soya, Nut, Gluten and Lactose free.

Administration and dosage

Suggested intake: Add 2 scoops Nestlé Nutrition Flavour Mix per 100ml.

Shelf life and storage

Shelf life of 12 months from date of manufacture when stored at room temperature.

Contraindications

Not for intravenous use.

Not suitable for children under 3 year of age.

Precautions

To be used with caution in children between 3 and 5 years of age.

Suitable for use in children over 5 years of age.

Must be used under medical supervision.

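### Endpoint 10 does not say which adverse events it counts, and weight gain is a benefit in endpoint 7 but a steroid harm in Appendix 2

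*Combined protocol and SAP*

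**What the plan says.** The protocol's list under Secondary outcomes and endpoints frames all ten items as gains of one arm over another: "To determine the beneficial effect of 6 weeks of ECS as compared to CS in inducing". Item 7 is "Increase in body weight and improvement in nutritional status (increased levels of micronutrients"; it sets no threshold and is not limited to underweight patients. Item 6 is a fall in anxiety or depression scores. Item 10 is, in full, "Decreased number of adverse events", with no form, time window or attribution rule. Hypothesis 2 uses the same idea for a different contrast: the short-course arm (ECSC) "will have similar efficacy than ECS and reduced number of adverse events".

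The checklist is headed "Appendix 2-Steroids adverse events assessment (visit 2". It has 22 items, each with a yes/no column and a comments column. They include weight gain (4), increased appetite (5), anxiety or nervousness (10), depression (11) and diarrhea (18). Nothing on the form records baseline status, worsening or cause. The Lay Abstract describes the disease as "characterized by diarrhea, abdominal pain and bleeding", and the Background says "Crohn's disease (CD) is characterized by inflammation of the gastrointestinal (GI) tract, diarrhea, pain and rectal bleeding".

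Handling of adverse events sets out a separate general process. Every event is recorded whether or not it is thought related, with intensity, seriousness and relationship to the study product. Neither that section, nor endpoint 10, nor Hypothesis 2 refers to Appendix 2.

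**The concern.** The same observation, a patient who gains weight, supports ECS under endpoint 7 and can be recorded as a steroid harm on the checklist. Diarrhea on the checklist may be the disease rather than the drug, and the mood items repeat what endpoint 6 measures. No rule in the plan says how these are classified when adverse events are counted.

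At stake is what a difference in adverse events between arms would mean. An arm that restores weight could look more toxic, and an arm that controls the disease better could look less toxic, with no difference in steroid toxicity in either case. The pilot is meant to supply effect estimates for planning a larger trial, so an ambiguous adverse-event measure would be carried into that planning.

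**Working it through.** The plan gives no rate or count for adverse events, so it has no figure of its own to reproduce here. The check is textual first, then an illustration of size.

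**Overlap supported by the documents**
- Weight: a benefit in endpoint 7, a harm in checklist item 4. Increased appetite (item 5) is grouped with it as a matter of judgement.
- Diarrhea: a disease feature in the Lay Abstract and Background, a harm in item 18.
- Mood: measured in endpoint 6, and again in items 10 and 11.

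That is 5 of 22 items: 5/22 = 23%.

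**Which contrast is affected**
- ECS against CS: the Intervention section gives both arms the same prednisone regimen. Only ECS receives formula, and its volume is adjusted after 3 weeks according to weight change. A difference in weight gain may therefore be the intended nutritional effect.
- ECSC against ECS: both arms receive formula, so formula-driven weight gain should be roughly balanced. The steroid course differs, so a difference in weight gain could here be a real steroid effect. Disease symptoms disturb this contrast only if efficacy differs.

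**Timing**
Study design places visit 2 before treatment, at randomization. Prednisone in the previous 30 days is an exclusion. A yes at visit 2 therefore cannot come from study prednisone, and no later use of the form is stated.

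**Size: diarrhea alone**
Shift in mean count = number of items × (prevalence in non-remitters − prevalence in remitters) × difference in remission. The prevalences and the 20-point remission difference are assumptions.
- Central: 1 × (0.60 − 0.20) × 0.20 = 0.08 items per patient
- Low: 1 × (0.50 − 0.25) × 0.20 = 0.05
- High: 1 × (0.70 − 0.15) × 0.20 = 0.11
- Equal remission: 1 × (0.60 − 0.20) × 0 = 0

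The arm with more remission gets the lower count.

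**Size: weight gain and diarrhea together**
The shift in mean count (ECS − CS) is the sum of the item risk differences. Assume weight gain is 10 to 40 points more frequent under ECS and diarrhea 0 to 30 points less frequent.
- Lowest: 0.10 − 0.30 = −0.20
- Highest: 0.40 − 0 = +0.40
- Equal and opposite, for example 0.30 − 0.30 = 0

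The direction cannot be predicted.

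**Scale**
With 30 per arm (Statistical analysis), the 95% half-width for one item's risk difference is 1.96 × √(2p(1 − p)/30). This is 0.20 at p = 0.20 and 0.25 at p = 0.50. The diarrhea shift alone is well inside that; a large weight-gain difference need not be.

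**The case against.** The strongest reply is that endpoint 10 is never tied to Appendix 2. The process the plan describes is the general one, with a relationship field for each event, and counting all events regardless of cause between randomized arms is a legitimate choice. A form labelled for a pre-treatment visit cannot penalise any arm. The sizes rest on assumed prevalences, and this is the tenth secondary endpoint of a pilot.

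Much of this stands, and it rules out three stronger readings:
- A reader might infer that endpoint 10 is the checklist total and is therefore already mixed. No section says so; the endpoint is undefined, and the mixing is conditional.
- A reader might add bloating, fatigue, joint pain and nausea/vomiting as disease symptoms, making 9 of 22 items (41%) and a shift of 5 × 0.40 × 0.20 = 0.40. Of those five symptom items, the documents name only diarrhea as a feature of the disease, so the supported figure is 0.08.
- A reader might conclude that the adverse-event part of Hypothesis 2 is undermined. That hypothesis expects similar efficacy in two arms that both receive formula; with equal remission the diarrhea shift is 0.

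The rest does not remove the problem. No rule links the relationship field to endpoint 10. Two arms receive both formula and prednisone, and treatment is unblinded, so judgements of cause could differ by arm. An all-events count is valid as a total, but without a further rule it cannot be read as steroid toxicity.

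**Conclusion.** The point holds in conditional form. The plan classifies weight gain in two opposite ways, places a disease symptom and two mood items on a steroid-harm form, and leaves the source of endpoint 10 unstated. If the checklist, or all recorded events, supply the count, an ECS–CS difference cannot be attributed to toxicity.

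The size from diarrhea alone is small: about 0.08 items per patient (0.05 to 0.11) under the stated assumptions. Weight gain could add more, in the opposite direction. As labelled, the checklist cannot measure on-treatment harm at all. The primary outcome and the sample size are unaffected. This is an inexpensive improvement worth making before data are collected.

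**What to change.** 1. State in endpoint 10 which form is counted and over what period.
2. Keep the visit 2 checklist as the baseline and repeat it at visit 3, where symptoms are already re-assessed. Ask about the whole interval since visit 2, because the short-course taper in Figure 1 ends well before visit 3.
3. Count an item toward endpoint 10 only if it is new or worse since visit 2.
4. Report weight gain and appetite (items 4 and 5) beside endpoint 7. Report diarrhea (18) and mood (10 and 11) separately from the steroid-specific items. Show the total as well, so that nothing is hidden.
5. Leave the endpoint 7 population unchanged. Limiting weight gain to underweight or malnourished patients would narrow an efficacy endpoint and reduce the usable number per arm, and this point does not require it.

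The cost is a few lines of protocol text, one repeat of an existing form with a tick for new or worse, and a smaller event count.

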Patients will be instructed to take the allocated treatment and to collect empty bottles/blisters of medication to assess the compliance at the next visit. Six weeks later (visit 3), their symptoms will be re-assessed, blood, urine and stool samples collected and SHAPE study performed. Patients will be instructed to stop the EEN or decrease the dose of CS, as detailed in the section “Follow up after treatment”. In the last visit (4th visit; 10 weeks after enrollment) we will collect information on symptoms, stool samples and urine.

The study protocol will be submitted by the investigator for approval by the Hamilton Integrated Research Ethics Board (HiREB).

Randomization process

The sequence of the treatments will be randomly generated using a computer-based pseudo-random number generator (RStudio Team (2015). RStudio: Integrated Development for R. RStudio, Inc., Boston, MA) Patients will receive one of challenges A,

B, or C consisting of CS, ECS or ECSC. A third person not involved in the study will perform the randomization to preserve treatment allocation concealed from participants and study staff. A block randomization will stratify patients by disease location (colonic/small bowel involvement). Each treatment will be assigned a number according to the randomization sequence. On recruitment, the patient will be assigned into one of three strata and given the next consecutive randomization number available for that stratum. Treatment will be not blinded for patients or study staff.

Subject recruitment

Subjects will be recruited from McMaster University Medical Centre (MUMC) Digestive Diseases Clinic, identified in an ongoing database organized in 2008 and by recruitment flyers posted at McMaster University Medical Centre, Juravinski Hospital and Hamilton General Hospital. Patients in the database signed an informed consent agreeing to be contacted for future research. Patients will be contacted by study personnel and invited to participate in the study.

After the subject has provided written consent to participate, an inclusion checklist will be completed. Subjects will be enrolled after having fulfilled all inclusion criteria, and none of the exclusion criteria.

Participants

One hundred adult patients diagnosed with IBD will be recruited at McMaster University Medical Centre. This will provide 30 subjects in each treatment arm, allowing for 10% dropout rate.

Inclusion criteria:

1. Adult patients (age 18-75 years)

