Following the completion of the period of exclusive enteral feeding, patients receiving EEN will be instructed to gradually reintroduce foods by adding one individual item every 2 days as shown in Table 1 ^{32,33} and Appendix with instructions for food introduction with coincident reduction of formula volumes under the supervision of an expert in Nutrition. The accelerated introduction of foods was based on a recent study showing similar results with additional benefits of 2 days vs 4 days ³³.

Treatment compliance

The subjects will be asked to keep the cans of Modulen and blister packs of prednisone during the entire treatment period and bring them back to the investigator at the end of that period. Compliance will be recorded in the CRF. In order to improve assessment of patient's compliance, 2 copies of a paper sheet diary will be provided at Visit 1. Patients

consuming <80% of the prescribed treatment dose throughout the study, or those who interrupted therapy for more than three consecutive days will be considered as noncompliant.

Measurements before and after treatment

- Clinical data regarding demographics, disease location and activity (Harvey-Bradshaw Index), social life and habits, past and current clinical medical background, previous surgeries, nutritional status (malnourishment, weight/ height) will be collected in CRF.
- Dietitian/ Certified nutrition support clinician: Dietary habits and caloric intake will be recorded at baseline with nutritional assessment during visits
- Bloodwork to assess for inflammatory markers, CRP, fecal calprotectin, ESR, as well as CBC, platelets, micronutrients (albumin, vitamin D, B12, A, zinc, copper, chromium)
- Questionnaires: McMaster Food frequency questionnaire(Hamilton, ON), quality of life (SIBDQOL¹³), disease activity (CDAI), anxiety and depression (HAD score, Beck inventory), and nutritional assessment (Subjective Global Assessment¹⁴ Braun Nutriscreen program)
- Gastrointestinal transit (colonic transit: SHAPE study and orocecal transit^{24,25}: patient will take one capsule and have an x ray on day five, following R.C. Evans, et al protocol, where ≥ 6 markers indicate delayed transit, therefore ≤ 5 is normalization of colonic transit).³⁴
- Stool sample (frozen samples) for microbiota composition (16S sequencing Illumina; Dr. [name]'s lab) metabolomics and metagenomics ([name]?)¹⁵

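### Secondary endpoint 7 takes any rise in micronutrient levels as better nutrition, with no baseline restriction or adjustment, and the Subjective Global Assessment has no assigned role

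*Combined protocol and SAP*

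**What the plan says.** Under Secondary outcomes and endpoints, item 7 compares ECS with CS at six weeks on "Increase in body weight and improvement in nutritional status (increased levels of micronutrients". It gives no amount of rise, reference limit or starting level.

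Two neighbouring items are tighter. Item 5, on colonic transit, has a marker cut-off and applies only "among those with altered transit at baseline". Item 6, on mood, asks for a "decrease >2 points HAD-A and/or HAD-D scores".

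Measurements before and after treatment lists the bloodwork as "micronutrients (albumin, vitamin D, B12, A, zinc, copper, chromium", which is seven analytes. The same section says "nutritional status (malnourishment, weight/ height) will be collected in CRF" and, among the questionnaires, names "nutritional assessment (Subjective Global Assessment¹⁴ Braun Nutriscreen program". No endpoint uses the last of these.

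On timing, Study design places bloodwork at the screening visit and again at week 6: "Six weeks later (visit 3), their symptoms will be re-assessed, blood, urine and stool samples collected and SHAPE study performed".

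Statistical analysis allows counts, means or medians and names a t test or Mann-Whitney test for differences between means. Its only regression model concerns symptomatic response and microbiota. It does not mention adjustment for baseline levels.

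**The concern.** Nothing in the eligibility criteria requires malnutrition or a low micronutrient level, and stable vitamin supplements are permitted with the formula. Some patients will therefore probably start within range for a given analyte. On the wording of item 7, a rise in such a patient is improved nutritional status. If the analysis is a comparison of levels, these patients stay in the average and pull the difference towards whatever happens in people with nothing to correct.

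The pilot's stated aim is to give effect sizes with confidence intervals for planning a larger study. An estimate that mixes correction of deficiency with movement in replete patients is hard to interpret for that purpose. With 30 per arm, an unadjusted comparison also carries any chance baseline difference in the analyte.

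**Working it through.** **The plan's own figure.** Participants and Statistical analysis give 30 evaluable patients in each of three arms with 10% dropout: 90 / (1 − 0.10) = 100, as stated. This does not depend on item 7.

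**Dilution.** Inputs: 30 per arm (Participants). The share below range at baseline, f, is not in the documents, so I assume 0.2 to 0.5. For illustration, take one analyte. Assume that among patients below range 90% rise on ECS and 50% on CS, and that among the rest 50% rise in each arm.

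- Difference over all patients = f × (0.90 − 0.50) = 0.40f.
- 95% half-width with n per arm, taking both proportions as 0.5 (widest case) = 1.96 × √(2 × 0.25 / n).
- For n = 30: 1.96 × √(0.5/30) = 0.253, or 25 points.

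| f | n per arm below range (30f) | Difference, all patients | Half-width, all | Difference, below range | Half-width, below range |
|---|---|---|---|---|---|
| 0.2 | 6 | 8 points | 25 | 40 points | 57 |
| 0.3 | 9 | 12 points | 25 | 40 points | 46 |
| 0.5 | 15 | 20 points | 25 | 40 points | 36 |

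The factor f applies equally to a difference in mean levels if the mean effect in replete patients is zero. Restricting to patients below range multiplies the difference by 1/f and the half-width by 1/√f, so the ratio of the two improves by 1/√f: 2.2, 1.8 and 1.4 for the three rows. The subset estimate is still imprecise. If treatment raised levels equally in everyone, the subset would only lose precision, which is why both analyses are worth reporting.

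**Baseline adjustment.** The standard error of a chance baseline difference is √(2/30) = 0.258 SD. The correlation between baseline and week 6, r, is not given; I assume 0.3 to 0.8.

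- An imbalance of one standard error shifts an unadjusted comparison of week-6 levels by r × 0.258 SD: 0.08 (r = 0.3), 0.13 (r = 0.5) and 0.21 SD (r = 0.8).
- Adjustment removes this shift and multiplies the residual variance by 1 − r²: 0.91, 0.75 and 0.36.

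**The case against.** The strongest reply is that item 7 is measurable as it stands and belongs to a pilot. The micronutrients are named in the measurements section, and body weight appears both there and in the endpoint. The increase may simply state a direction, as the quality-of-life item does, with mean levels then compared between arms. This is one of ten secondary outcomes, and none of the three hypotheses names nutrition. All of that stands and limits the weight of the point. It does not supply a baseline restriction or adjustment.

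Four stronger readings are tempting, and the documents do not support them:

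- **A rival definition of nutritional status.** The line on malnourishment, weight and height lists what goes into the case report form. It does not define an endpoint.
- **An endpoint that can come out almost anywhere.** If improvement were a yes/no call per patient and each of seven independent analytes were equally likely to rise or fall, an unchanged patient would qualify with probability 1 − 0.5⁷ = 99.2% if any one had to rise, and 0.5⁷ = 0.8% if all had to. The plan never states such a rule.
- **Bias towards ECS.** Chance rises are expected equally in all randomised arms, so under any one fixed rule the expected null difference is zero.
- **Inflated false positives.** The best of nine independent measures at an assumed two-sided 0.05 gives 1 − 0.95⁹ = 37% for any significant result, or 1 − 0.975⁹ = 20% for a favourable one. Both need selective reporting, which no section plans; the general aim promises estimates for all measures of interest.

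**Conclusion.** The point holds as a gap in one secondary endpoint. Item 7 accepts any rise from any starting level, although item 5 in the same list restricts to patients abnormal at baseline and item 6 sets a minimum change. The analysis section offers only unadjusted two-group tests for these levels, and the Subjective Global Assessment is collected without a stated use.

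The consequence is a nutritional estimate that is hard to interpret and probably diluted: 20% to 50% of the below-range effect would remain if 20% to 50% of patients start below range and the others cannot benefit. Both conditions are assumptions. Collecting the Subjective Global Assessment without making it an endpoint is not in itself an error, and listing albumin among the micronutrients is only a matter of labelling. The primary endpoint and the total of 100 do not change.

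**What to change.** Amend item 7 and Statistical analysis together:

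- For every analyte listed under Measurements before and after treatment, report the ECS versus CS difference in week-6 level, adjusted for that analyte's baseline level, with a confidence interval. Name the blood sample that serves as baseline; the only pre-treatment bloodwork described in Study design is at screening.
- For each analyte, also report the proportion corrected to the laboratory range among patients below range at baseline, as item 5 does for transit, with the number of such patients in each arm.
- Report body weight and the Subjective Global Assessment as separate outcomes. The assessment should not become the sole definition of improvement: it is a subjective rating, treatment is not blinded, and patients already well nourished cannot improve in category.
- State that all these results will be reported and that no measure will be selected after data are seen.

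The cost is protocol wording and a simple regression per analyte, since the data are already planned. The downside is that the below-range subsets will be small, perhaps 6 to 15 per arm under the shares assumed above, so those proportions should be presented as estimates with wide intervals.
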